## 1.0 – INTRODUCTION

### 1.1 – Background

Technological improvements are ongoing in minimally invasive surgery. Laparoscopic surgery has allowed for enhanced patient comfort and recovery in numerous procedures including cholecystectomies, gastric bypasses, and laparoscopic renal procedures. Laparoscopic surgeries must insufflate the abdomen in order to perform the necessary procedures of the surgery. In order to maintain space and vision, carbon dioxide (CO2) must be used to inflate the abdomen with trocars being used as the entry points to the abdomen. These trocars are then connected to insufflation systems to increase intraabdominal volume. Many different trocars have been used historically to accomplish this task at OhioHealth, with recent focus on valve-less trocars. Since its FDA clearance, the AirSeal system has been used routinely in centers throughout the United States, including OhioHealth Dublin Methodist Hospital. The AirSeal system has been observed by surgeons and anesthesia teams to provide a more gentle, stable, and consistent pneumoperitoneum.

The AirSeal System consists of an insufflation, filtration, and recirculation system (AirSeal iFS), a triple lumen filtered tube set, and a valve free trocar (AirSeal Access Port). The device enables peritoneal access with a novel mechanism to maintain pneumoperitoneum without a mechanical seal. Specifically, the AirSeal System creates a pressure barrier within the proximal housing of the cannula which acts as an invisible seal to maintain pneumoperitoneum during the course of surgery. It utilizes a re-circulation and filtration control unit (AirSeal iFS) designed specifically for the AirSeal Access Port to create and maintain the pressure barrier. The AirSeal iFS is reusable and the AirSeal Access Port and triple lumen filtered tube set are designed as single patient use devices. The AirSeal System has applications in minimally invasive abdominal surgical procedures to establish a path of entry for laparoscopic instruments. The lack of a physical valve allows the AirSeal port to vent immediately in the event of any pressure spikes, as the port has a constant opening where the pneumoperitoneal gas may escape to keep pressures down.

Since first described in 2001, robotic assisted laparoscopic prostatectomy (RALP) has been traditionally performed at a pneumoperitoneal insufflation pressure of 12-15 mmHg, derived from standard practice used during laparoscopic surgeries. Abdominal insufflation with carbon dioxide causes a multitude of known physiologic changes including increased peak airway pressures, depressed cardiac output, oliguria, and systemic acidosis, many of which show dose-dependent improvement with the reduction of intraoperative pressures.

Reducing intraperitoneal stretch with lower intra-abdominal pressures may also improve postoperative pain and facilitate earlier hospital discharge as evidenced by studies in general surgery comparing outcomes following laparoscopic cholecystectomy. Despite these results, few surgeons perform RALP at reduced pressure likely due to habit or the perceived concern for poorer visibility, compromised hemostasis, and/or technical difficulty. Furthermore, some have even proposed performing RALP at an increased pressure of 20 mmHg in an effort to achieve better hemostasis despite other physiologic consequences. There remains a paucity of data exploring the feasibility and potential benefits of performing RALP at low insufflation pressures, and no studies have explored how high the pneumoperitoneal pressure must be to perform RALP or, in other words, the minimum pressure that is adequate.

We plan to examine the impact of low pressure during RALP with the intention of identifying whether lower pressures might benefit patients. We hypothesize that a low insufflation pressure may provide an improvement in postoperative pain and abdominal distension in addition to potential physiologic benefits, and that these factors might then allow a shorter hospital stay. We previously initiated a protocol in September of 2016 (IRB# 1066864) to perform RALPs at an insufflation pressure of 6 mmHg with the intention of increasing the pressure as needed on an individual patient level. In order to determine whether this might allow earlier discharge when successful, we began allowing for same-day discharge in patients meeting appropriate criteria. Having now demonstrated feasibility in over 300 consecutive patients using this ultralow pneumoperitoneum protocol, we now plan to conduct a randomized trial to compare a pressure of 6 mmHg with patients having RALP at a standard pressure of 15mmHg to determine whether there is a true benefit.

### **1.2 – Specific Aims/Rationale**

We propose a study comparing insufflation pressures during RALP. Standard pressure is typically 15 mmHg, while in our previous study we determined that 6 mmHg is possible routinely. Therefore, we plan to compare the clinical outcomes of patients at a pneumoperitoneal pressure of 15 versus 6 mmHg.

***Aim #1)*** Compare average postoperative pain medication use between groups, as measured in total morphine equivalents (MME) over time at pre-specified time intervals through follow-up at 1 week.

***Aim #2)*** Compare average and maximum postoperative pain scores between groups, as measured using the self-reported 11-point numerical rating scale (NRS), over time at pre-specified time intervals through discharge.

Time intervals for Aims #1 & 2 are as follows: during the post-anesthesia care unit (PACU) stay, the first 4 hours on the floor, next 8 hours, and the following 8 hours; as well as the final score immediately prior to discharge.

***Aim #3)*** Compare operative ventilation as measured by average tidal volume (ml) between groups.

Tidal volume is the lung volume representing the normal volume of air displaced between normal inspiration and expiration when extra effort is not applied (i.e., normal/resting breathing), and is measured continuously throughout the procedure by Anesthesia. Potential patient benefits to a lower pneumoperitoneal insufflation pressure include decreased postoperative pain and improved intraoperative ventilation.

***Aim #4)*** Compare average length of stay (typically 0-1 days) between groups.

## **2.0 – METHODS**

## 2.1 – Study Population

The study population will include males age 18 or older with prostate cancer who are eligible and electing to undergo robotic assisted laparoscopic prostatectomy (RALP) at OhioHealth Dublin Methodist Hospital (DMH) Robotic Urology with the Principal Investigator (PI). We anticipate that enrollment of 192 patients (96 in each group) will take a minimum of 1 year to complete. See section 2.4 (Statistical Analysis) for the details of the sample size calculation.

Exclusion criteria for RALP include:

1. Cirrhosis or liver failure (Child-Pugh class A, B, or C) or clinical suspicion of liver failure
2. Ascites
3. Uncontrolled diabetes [as reported by the pre-anesthesia testing (PAT) physician]
4. Renal insufficiency (serum creatinine level > 3.0 mg/dl)

Exclusion criteria to participation in this study include:

1. Age < 18
2. Emergency surgery
3. Patients with a significant preoperative dependence on narcotic medications
4. Unable to give informed consent
5. Dementia, history of dementia, or other significant mental impairment that would, in the opinion of the investigator, impede patient self-reporting
6. Persons participating in any other research study involving an investigational drug or device or investigational surgical procedure that could interfere with the physiologic parameters being collected (for example, a study evaluating different anesthesia regimens that could confound study results)
7. Non-English-speaking or reading

## 2.2 – Study Variables & Outcomes of Interest

The following data points will be collected for patients who choose to receive treatment and consent to this study at OhioHealth Dublin Methodist Hospital (see Table 1). Patient data will be collected via Epic/CareConnect, as well as by means of study specific Data Collection Forms (DCFs; see Appendices A-D). Only the designated study staff will have access to the REDCap database and paper DCFs created solely for use in this study. Patient data will be de-identified upon study completion, prior to statistical analysis.

**Table 1. Study Variables.**

Category	Data points
Enrollment Log	

1. MRN

2. Name

3. DOB

4. Date of consent

5. DOS/randomization

6. Enrolled (y/n)

7. Randomized (y/n)

	

8. Randomization envelope (#)

9. Withdrawn (y/n)

10. Reason withdrawn (if applicable)

Demographics	

1. Phone number

2. BMI (kg/m^2)

3. Weight (lbs)

4. Medical history (free text)

5. Surgical history (major only; free text)

6. Serum creatinine (most recent prior to surgery) (mg/dl; date)

7. Hemoglobin (most recent prior to surgery) (g/dl; date)

Intraoperative	

1. Details of the surgical procedure (free text)

2. Port number/size(s)/locations (standard protocol -or- deviation from standard protocol) – if deviation, explain

3. Continuously recorded values (only means/standard deviations recorded in REDCap) – as measured by Anesthesia

a. End tidal CO2 (mmHg)

b. O2 saturation (%)

c. Respiratory rate (bpm)

d. Blood pressure (mmHg)

e. Heart rate (bpm)

f. Tidal volume (ml)

g. PIP (peak inspiratory pressure) (mmHg)

h. PEEP (positive end-expiratory pressure) (mmHg)

4. Core body temperatures (F) – as measured by Anesthesia

a. After trocar placement (baseline)

b. 30 minutes

c. 60 minutes

d. End of procedure

5. Insufflation time (minutes)

6. Insufflation pressure (6 or 15 mmHg)

7. Increased pressure episodes necessary to successfully complete the procedure (# times)

a. Time of each adjustment (hh:mm)

b. Level of each adjustment (mmHg)

8. Significant loss of pneumoperitoneum (# times)

a. Time of each adjustment (hh:mm)

b. Level of each adjustment (mmHg)

9. Pressure range (lowest and highest; mmHg)

10. Smoke evacuation quality (below average, average, above average)

11. Total amount of gas used during the procedure (l)

12. Scope cleanings (#)

13. Malfunctions of the AirSeal iFS or control devices (# times)

	

14. Estimated blood loss (EBL; ml)

15. Obturator artery manipulation (no, left, right, bilateral) – only on Case Sheet (Appendix F)

16. Console time (minutes from initial incision to closure)

17. Use of intraoperative pain medication

a. Fentanyl (y/n)

i. Dose (mg)

ii. Morphine equivalents (MME)

b. Toradol (y/n)

i. Dose (mg)

18. Pathology report

a. Pathological Stage

b. Clinical Stage (T1a-c, T2a-c, T3a-c)

c. Gleason Score (ranging from 6-10: 3+3=6, 3+4=7, 4+3=7, 3+5=8, 5+3=8, 4+4=8, 4+5=9, 5+4=9, 5+5=10)

d. Margins (positive/negative)

e. Extra prostatic extension (EPE; y/n)

f. Tumor quantification (%)

Postoperative (PACU & Floor)	

1. Recorded in PACU

a. Vital signs recorded in PACU setting

i. Time

ii. Respiratory rate (bpm)

iii. Blood pressure (mmHg)

iv. Heart rate (bpm)

v. Temperature (F)

b. Other PACU assessments

i. O2 saturation (%) (first recorded)

ii. Post-operative nausea and vomiting (y/n for each)

iii. Wound infection (y/n)

c. Time in PACU (hours)

i. Arrival & discharge times (hh:mm)

2. Recorded on Floor

a. Vital signs first recorded in non-PACU setting (i.e., on the floor)

i. Respiratory rate (bpm)

ii. Blood pressure (mmHg)

iii. Heart rate (bpm)

iv. Temperature (F)

b. Other non-PACU / Floor assessments

i. Labs drawn (y/n)

1. Serum creatinine (mg/dl; date)

2. Hemoglobin (g/dl; date)

	

ii. Wound infection (y/n)

c. Length of stay (days; typically 0 to 1)

i. Discharge date/time (m-d-y; hh:mm)

3. Use of postoperative pain medication

a. Opioids (y/n for each: fentanyl, Dilaudid, oxycodone, Norco, tramadol, Percocet, Demerol)

i. Morphine equivalents (MME)

b. Non-opioids (y/n for each: Toradol, Tylenol, oxybutynin)

4. Postoperative pain scores (0-10; asleep, missed, or discharged)

a. Average and maximum scores during each interval (during the PACU stay, the first 4 hours on the floor, next 8 hours, and the following 8 hours; as well as the final score immediately prior to discharge)

b. At each location (abdomen, legs, groin, scrotum, shoulder, other/specify)

5. Timing of ability to pass gas (day 0, day 1, day 2, >day 2)

6. Clinically-significant ileus (i.e., requiring treatment; y/n)

Follow-Up (1 week, 1 month, & 3 months)	

1. QoR-15 (0-150) – only asked at week 1

a. Collected (y/n)

b. Score (0-150)

2. Prescription(s) given (y/n) – only asked at week 1

a. Prescription(s) filled (y/n)

b. Opioids (y/n for each: fentanyl, Dilaudid, oxycodone, Norco, tramadol, Percocet)

i. Number of pills taken for each (#)

ii. Morphine equivalents (MME)

c. Non-opioids (y/n for each: Toradol, Tylenol, oxybutynin)

3. Scrotal swelling (y/n) – only asked at week 1

4. Leg weakness (y/n)

a. Left, right, bilateral

b. Degree of weakness (each leg; mild, moderate, severe)

c. Impaired ability to walk

d. Impaired ability to drive

We will collect information on pertinent surgical outcomes that occur through discharge. The average amount of time spent in the PACU is roughly 1-2 hours, and the average hospital length of stay is 0-1 days. For Intraoperative Item #2, a deviation from the standard port number/size(s)/locations would be due to body habitus, and will not have an effect on clinical outcomes. For Intraoperative Item #3, continuous values will be exported into individual patient-specific Excel spreadsheets with the assistance of the CareConnect Systems Analysts. This is due to the fact that there are far too many data points (8 different variables every 1 minute for 120 minutes) to be manually extracted and subsequently manually entered. The PI will perform individual analyses on these data sets in conjunction with Analysts, and

calculate means and standard deviations to be entered into REDCap. For Intraoperative Item #15, we are collecting whether the obturator artery was affected for each leg, as this could potentially be a confounder to postoperative leg pain (i.e., increased pain in the affected leg). Finally, the presence of wound infection (in the PACU and on the Floor; Postoperative Items #1b-iii and #2b-iii, respectively), as well as clinically-significant ileus (on the Floor; Postoperative Item #6) will be evaluated and assessed by nursing staff per routine care and entered into the medical record.

The Quality of Recovery (QoR)-15 questionnaire (Appendix E) is used to evaluate recovery from anesthesia. The tool consists of 15 questions that assess patient-reported quality of postoperative recovery using an 11-point (i.e., 0-10) numerical rating scale, where "0" refers to "all of the time [poor]" and "10" refers to "none of the time [excellent]." Therefore, a higher score refers to better quality of recovery. The questionnaire assesses basic and essential activities of daily life (ADLs), pain, emotions, and personal/overall well-being, among others. The survey will be administered at the 1-week follow-up visit only, and takes approximately 2-3 minutes to complete.

The Physician Case Sheet (Appendix F) is a routine form used in the operative suite by the PI. In the case of research-related data that is not otherwise recorded intraoperatively, certain data points are added for research purposes so the surgeon/PI is reminded to document. For the purposes of this study, we have added "obturator artery affected (no/left/right/bilateral)," as this is not collected consistently, and could be a confounder to our secondary outcome of pain scores (specifically for the affected leg/s, as applicable).

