will be educated on the importance of bringing all medications to follow-up visits, which will lead to more accurate pain medication counts and calculations.

Patients are typically discharged on Day 0-1, and for those discharged on Day 0 (i.e., same-day), the CRC will call the following morning to evaluate pain (see Appendix C). Because we are targeting same-day or next-day discharge, there is the potential for missing data in the first 24-hour period. Therefore, there will be no restrictions or protocol deviations for pain scores, as we are collecting scores only while inpatient/awake and via phone call for those discharged same-day. Follow-up visits per routine care occur at approximately 1 week postoperatively for catheter removal, as well as at 1 month and 3 months. Appointments will follow routine scheduling practices for the office, which may include variance in exact visit timing. Generally, patients will have 1 week postoperative visit around 5-7 days after surgery, but may be delayed further by approximately 1 week depending on scheduling availability and/or clinical indication (e.g. need for cystogram). Follow-up visits are generally 1 month and 3 months post-surgery, but may occur approximately a couple weeks before or after as per physician standard of care scheduling to accommodate patient and physician availability. There will be no strict visit windows to allow for visit scheduling flexibility. Because the majority of RALP patients will be eligible for participation, schedulers will be educated on the importance of return visit timing accuracy. There will be no extended or long-term follow-up via direct patient contact or EMR review.

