Patients that are unable to pass gas while inpatient will be called on postoperative day 1 (if discharged same-day only) and day 2. The post-operative day 1 phone call will also be utilized to assess pain for those who were discharged same-day, as explained above. If a patient confirms that they have passed gas on day 1, they will not be called again on day 2. For Thursday/Friday procedures where days 1 and/or 2 (as applicable) fall on the weekend, patients will be called on Monday morning and asked to recall when they were able to pass gas (i.e., whether it occurred on Saturday or Sunday). If patients are not discharged same-day, they will only receive a single phone call on day 2 if they did not pass gas prior to discharge. Patients who are not discharged same-day and are able to pass gas prior to discharge will not receive any phone calls. In the case that a patient is still unable to pass gas on day 2, we will repeat phone calls daily until they are able to do so, although we do not anticipate many patients will need to be called past day 2. We are collecting this data due to recent anecdotal evidence in Robotic Urology that patients who receive Percocet were able to pass gas on average in 1.6 days versus 1.4 days for those that did not receive Percocet.

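### Ileus requiring treatment is recorded only during a 0-1 day floor stay, so later cases are under-recorded over a window that ends at discharge, itself a trial outcome

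*Combined protocol and SAP*

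**What the plan says.** Table 1 in section 2.2 lists, as Postoperative item 6, "Clinically-significant ileus (i.e., requiring treatment; y/n". The item sits in the block for the PACU and floor. The text after the table fixes who records it and where: "clinically-significant ileus (on the Floor; Postoperative Item #6) will be evaluated and assessed by nursing staff per routine care". The same text sets the general window: "We will collect information on pertinent surgical outcomes that occur through discharge".

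That window is short. Section 2.2 states that "the average hospital length of stay is 0-1 days", and section 2.3 that "Patients are typically discharged on Day 0-1".

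After discharge, the Follow-Up block of Table 1 lists the QoR-15, prescriptions, scrotal swelling and leg weakness. It does not list ileus. Section 2.3 describes telephone calls about passing gas (and, after same-day discharge, pain), repeated daily if needed until gas is passed. Below Table 3, section 2.3 says that non-serious treatment-related adverse events are not tracked, and that treatment-related serious events are followed for 90 days after discharge by chart review.

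The only bowel-recovery figures are in section 2.3: "patients who receive Percocet were able to pass gas on average in 1.6 days versus 1.4 days for those that did not receive Percocet". The protocol describes their source as "recent anecdotal evidence in Robotic Urology".

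**The concern.** The plan follows passing of gas beyond discharge but, as described, stops looking for ileus at discharge. A patient who goes home on day 0 or 1 and is treated for ileus on day 3 has no listed field in which to be recorded.

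Two things follow. The recorded rate will understate the true rate in both arms. The length of observation also depends on discharge day, which is compared between arms under Aim 4 and which section 1.1 suggests may be earlier at low pressure. If so, the arm watched for less time will show less ileus even when the true risks are equal. Section 2.4 says clinical outcomes will be compared between pressures, and section 2.3 hopes the results will encourage lower pressures in laparoscopy generally. A favourable ileus count could therefore be read as evidence of benefit or safety.

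**Working it through.** **Plan's own figure.** There is none to reproduce: the documents state no ileus rate, onset time, power or sample size for ileus. The sample size in section 2.4 rests on pain scores at 5-12 hours.

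**Document check.**
- Place and assessor of the ileus item: floor, nursing staff, routine care (section 2.2).
- End of window: discharge, typically day 0-1 (sections 2.2 and 2.3).
- Later items: no ileus entry in the Follow-Up block (Table 1).
- Gas calls: as described, they ask about gas and pain. A patient kept overnight who passes gas before discharge gets no call (section 2.3).
- Chart review: treatment-related serious events only (section 2.3).

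On the text alone, ileus treated after discharge that is not serious, or not judged treatment-related, goes unrecorded.

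**Illustration of the possible imbalance.** All inputs are assumed except the 10-point difference in day-0 versus day-1 discharge that section 2.4 calls clinically significant, and the 96 patients per arm in section 2.1. Let p be the proportion discharged the same day, c0 the fraction of eventual ileus visible before a day-0 discharge, and c1 the fraction visible before a later discharge.

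Captured fraction = p × c0 + (1 − p) × c1. With equal true risk, the false ratio is the captured fraction at 6 mmHg divided by that at 15 mmHg.

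| c0 | c1 | p = 0.5 (6 mmHg) | p = 0.4 (15 mmHg) | Ratio |
|---|---|---|---|---|
| 0 | 0.25 | 0.125 | 0.150 | 0.83 |
| 0 | 0.50 | 0.250 | 0.300 | 0.83 |
| 0.10 | 0.25 | 0.175 | 0.190 | 0.92 |
| 0.10 | 0.50 | 0.300 | 0.340 | 0.88 |

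For the last row: 0.5 × 0.10 + 0.5 × 0.50 = 0.300, 0.4 × 0.10 + 0.6 × 0.50 = 0.340, and 0.300 / 0.340 = 0.88. Across the table, 66% (1 − 0.340) to 87.5% (1 − 0.125) of cases are missed.

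A wider gap in discharge gives a lower ratio. At 60% versus 30% the same four settings give:
- 0.100 / 0.175 = 0.57
- 0.200 / 0.350 = 0.57
- 0.160 / 0.205 = 0.78
- 0.260 / 0.380 = 0.68

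**In numbers of patients.** With an assumed true ileus rate of 2-10%, each arm of 96 has 1.92 to 9.6 true cases. At 50% versus 40%, the recorded counts run from 1.92 × 0.125 = 0.24 versus 1.92 × 0.150 = 0.29, up to 9.6 × 0.300 = 2.88 versus 9.6 × 0.340 = 3.26. The largest gap between arms is 9.6 × (0.300 − 0.250) = 0.48 of a case.

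**The case against.** Several points on the other side are sound.

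- **Gas is not ileus.** A reader might infer from "able to pass gas on average in 1.6 days versus 1.4 days for those that did not receive Percocet" that most patients are scored negative before ileus could be recognised. The documents do not support that. The figures are anecdotal means without a standard deviation, are split by Percocet use and not by pressure, and measure passing of gas. Not having passed gas by day 1 is not ileus requiring treatment.
- **Coding is not stated.** No text says that a patient discharged early is coded as no ileus and not as missing. The item does offer only yes or no, whereas the pain scores have codes for asleep, missed and discharged, so the gap is real but its handling is unknown.
- **There are partial backstops.** A serious ileus judged treatment-related would be found by chart review. Bowel recovery itself can still be compared, because time to passing gas is followed after discharge. The limit applies to the ileus item only.
- **The imbalance is conditional.** Shorter stay at 6 mmHg is a hypothesis. The illustration also applies the overall same-day rate to patients who will develop ileus. Section 1.1 describes same-day discharge, under the preceding protocol, only for patients meeting criteria, so discharge may depend on how the patient is doing.
- **The forms are not available here.** The contents of the Post-Discharge and Follow-Up forms (Appendices C and D) are not in the text reviewed. An ileus question there cannot be excluded, although Table 1 and section 2.2 point against it.

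These points limit the size and certainty of the problem. They leave standing that the described window for ileus ends at discharge and that no listed item extends it.

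**Conclusion.** The point holds in a limited form. As described, the plan under-records ileus treated after discharge, apart from events caught as treatment-related serious events. The direction of any imbalance follows from the design: if one arm goes home sooner, that arm is observed for less time and looks better. The size cannot be derived from the documents. On the assumed capture fractions, the false ratio is about 0.83-0.92 with same-day discharge of 50% versus 40%, and lower if discharge differs more. At 50% versus 40% it amounts to less than one recorded case between arms.

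It would go too far to say that the 6 mmHg arm will show a spurious benefit, or that the trial cannot study bowel recovery. Ileus is in none of the four aims and does not drive the sample size, so the powered comparison is untouched. This is a minor point and a cheap improvement.

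**What to change.** In section 2.2, define the outcome as ileus requiring treatment from surgery through the 1-week visit, for every patient regardless of discharge day. Add one dated yes/no item to the 1-week Follow-Up form, asking about treatment for ileus since surgery, here or elsewhere, with a chart check when the answer is positive. State how patients without an assessment are coded. Compare arms on this item and report the floor-only value descriptively.

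Do not rely on the gas calls. Patients kept overnight who have passed gas are not called, so a question asked there would again depend on discharge day.

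In section 2.3, reconcile the statement that there is no extended follow-up by patient contact or EMR review with the 90-day chart review for serious events.

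The cost is one form item and a few sentences, with no new visit or procedure. The downsides are that post-discharge events are patient-reported, and that section 2.3 lets the 1-week visit slip by about a week, so the window will vary somewhat. Recording the date of each event lets the team check whether that matters.
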